6.0 STUDY ASSESSMENTS

6.1 Time and Event Table (Summary of Assessments)

	Screening	Baseline	Week 13	Week 25
Demographics	X			
Locator Form	X			
Prior and Concomitant Medications	X			
PAR-Q	X			
PHQ-9	X			
GPAQ	X			
QIDS-SR		X	X	X
SF-36		X	X	X
PSQI		X	X	X
BFI		X	X	X
FACT-B		X	X	X
Brief COPE		X	X	X
SHAPS		X	X	X
STAI		X	X	X
Relationship status		X		
Couples Satisfaction Index (CSI)		X		
MGH-ATRQ		X		
PASC-Q		X	X	X
PASE-Q		X	X	X
Blood draw		X	X	X
Accelerometer (activity and sleep)		X	X	X

6.2 Types of Assessments

6.2.1 Eligibility Screening Measures

Demographics Form. The demographics form will be administered to all participants at the baseline visit. The form consists of basic demographic information (e.g., gender, race/ethnicity, etc.).

Patient Health Questionnaire-9 (PHQ-9). The PHQ-9²⁰ is a 9-item scale designed to measure depressive symptoms. We will use the PHQ-9 to identify patients with elevations in depressive symptoms. Patients scoring 8 or higher on the PHQ-9 will be eligible for participation in the study. Large meta-analyses support the utility of the PHQ-9 in identifying MDD and assessing depressive symptom severity.^{21,22}

General Physical Activity Questionnaire (GPAQ). The GPAQ²³ is a 16-item scale designed to assess physical activity across three domains (work, transportation, and recreation). We will use the GPAQ to identify patients that do not currently meet physical activity recommendations of 150 minutes of weekly moderate-intensity physical activity.

6.2.2 Diagnostic and Screening Measures

Locator Form. The Locator Form will be used to obtain contact information for each participant. The Locator Form will be filled out at the screening visit and then routinely updated on a monthly

basis thereafter (excluding the final visit). In addition, a Locator Form may be completed/updated any time the participant reports a change in contact information.

Prior and Concomitant Medications. The Prior and Concomitant Medications form assesses prescribed medications taken by the participant. The Prior and Concomitant Medications form will be administered at the screening visit and then monthly thereafter, if the participant endorses a change in medication status.

Physical Activity Readiness Questionnaire-Revised (PAR-Q). The PAR-Q¹⁹ asks 7 health-related questions to determine whether a person needs to consult with their physician prior to engaging in an exercise program. The PAR-Q will be administered at the screening visit.

6.2.3 Study Assessments

Measurements of Physical Activity:

Actigraph GT3X+ accelerometer. – The Actigraph will provide a valid and reliable objective assessment of physical activity.²⁴ Subjects will be asked to wear the device for a 7-day period at each assessment time point (baseline and weeks 13 and 25). Subjects will be instructed to wear the device on their non-dominant arm and to remove the device only when it may become submerged in water (bathing, swimming, etc.). Following, the 7-day period, subjects will return the accelerometers using a postage-paid envelope.

Measurement of Psychosocial and Physical Outcomes:

Quick Inventory of Depressive Symptomatology – Self-Rated (QIDS-SR₁₆). The QIDS-SR₁₆²⁵⁻²⁷ is a 16-item questionnaire to assess severity of depression-specific symptoms. The QIDS-SR₁₆ has high reliability (Cronbach's alpha of 0.83), good concurrent validity (correlations between the QIDS-SR₁₆ and the 17-item Hamilton Rating Scale for Depression is 0.81)²⁵.

Short Form 36 Health Survey (SF-36). The SF-36²⁸ is a 36-item survey of patient-reported general health and quality of life across eight domains of well-being (physical functioning, social functioning, vitality, pain, general health, physical role functioning, emotional role functioning, and mental health).

Pittsburgh Sleep Quality Index (PSQI). The PSQI²⁹ is a 19-item scale designed to assess sleep quality and disturbances. Scores range from 0 to 21 with higher scores representing worse sleep quality. The PSQI has demonstrated reliability (Cronbach's alpha of 0.80) in the assessment of self-reported sleep quality and validity when compared to sleep diaries and polysomnography.³⁰

Brief Fatigue Inventory (BFI). The BFI³¹ is a 9-item scale designed to assess fatigue. The BFI demonstrates good reliability (Cronbach's alpha of 0.96) and validity (correlation of 0.86 with the POMS fatigue subscale).

Functional Assessment of Cancer Therapy – Breast (FACT-B) – The FACT-B³² is a 44-item scale designed to measure multidimensional quality of life in breast cancer patients. The FACT-B has demonstrated reliability (Cronbach's alpha of 0.90) and concurrent validity (0.87 correlation with the Functional Living Index-Cancer and 0.86 correlation with the Functional Assessment of Cancer Therapy-General).

Brief COPE. The Brief Cope³³ is a 28-item scale designed to assess a wide range of coping responses. The Brief COPE has been used in studies of cancer patients and demonstrates good reliability and validity.

Snaith-Hamilton Pleasure Scale (SHAPS). The SHAPS³⁴ is a 14-item scale that measures anhedonia, the inability to experience pleasure. The SHAPS has adequate construct validity, satisfactory test-retest reliability (ICC=0.70) and high internal consistency has also been reported (Cronbach's alpha of 0.94).

State Trait Anxiety Inventory (STAI). The STAI³⁵ is a 40-item scale that measures state and trait anxiety.

Anthropomorphic assessments. Height will be assessed at baseline. Weight and waist circumference will be measured at each assessment time point. Height and weight measurements will be used to calculate Body Mass Index (BMI).

Metabolic indices. Blood samples will be collected by a trained phlebotomist to allow for evaluation of markers of metabolic health, including blood glucose, triglycerides, and lipids.

Antidepressant Medication Use. The Massachusetts General Hospital Antidepressant Treatment History Questionnaire (MGH-ATRQ) will be assess the current use antidepressant medication.

Relationship Status. A single-item question will ask participants to indicate their current relationship status from one of 7 categories (single, never married; cohabiting with partner; married, living together; married, not living together; separated; divorced; widowed). The Couples Satisfaction Index (CSI)³⁶ is a 16-item form that captures relationship quality among participants who endorsed currently being in a romantic relationship. The CSI is a well-validated and reliable measure that draws from other previously established relationship satisfaction measures.

At the end of the program we will conduct a self-report questionnaire aimed at evaluation participants' satisfaction with the program. This questionnaire will include Likert-scale questions about: 1) satisfaction with the program; 2) program engagement/adherence; 3) program enjoyment; 4) perception of program effectiveness; 5) willingness to recommend program to others; 6) barriers to program participation; 7) intent to maintain physical activity; and 8) attitudes toward physical activity. This assessment will allow for further refinement of the intervention to ensure its sustainability and broad dissemination.

Psychological Mediators/Moderators of Physical Activity Behavior Change:

Physical Activity Stages of Change Questionnaire. The 4-item scale assesses the current stage within the Transtheoretical Model framework (Pre-contemplation, Contemplation, Preparation, Action, Maintenance). These stages are highly correlated with change in physical activity over time.³⁷

Physical Activity Self-Efficacy Questionnaire. The 3-item scale assesses self-efficacy for physical activity. Activity-specific self-efficacy is highly correlated with activity change and psychosocial outcomes.³⁷

6.2.4 Physiological Measures

Physiological Measures. Physiological measures include height, weight, body mass index (BMI) and waist circumference. Height will be obtained once at baseline and the other measures will be obtained at each assessment visit.

6.2.5 Safety Assessments

Assessments involved in determining participants' ability to safely participate in the protocol (maximal exercise testing, laboratory tests, and physical exam) are described under Diagnostic

and Screening Measures. Additionally, reportable AEs and all SAEs will require completion of an AE Form (and SAE form as applicable) to document and track reportable AEs.

7.0 STUDY TREATMENTS

7.1 Physical Activity Intervention

Print-based education

All participants will receive print-based education focused on physical activity. Provision of print-based materials can result in significantly increases physical activity as demonstrated in a study by Vallance et al.³⁸ in which breast cancer survivors who received the book, *Exercise for Health: An Exercise for Breast Cancer Survivors*, increased their physical activity levels by 70 minutes per week.³⁸ All subjects in the current project will be given a copy of *Exercise for Health: An Exercise Guide for Breast Cancer Survivors*,^{38,39} a 56-page book based on the theory of planned behavior. The book was developed and evaluated by experts in the field³⁹ and has been proven efficacious in increasing physical activity in breast cancer survivors.³⁸ Topics covered within the book include benefits of exercise in breast cancer survivors; recommendations on type, duration, frequency and intensity of exercise; goal-setting; and advice on overcoming common barriers.

Self-monitoring

Subjects will be provided with a commercially available activity monitor (i.e., Fitbit). The project interventionist will instruct subjects on proper use of the device and options for viewing the data collected by the device. Subjects will be instructed to wear the device daily. Those with access to smartphones or computers will be instructed to upload data on a regular basis for continuous self-monitoring. These devices are compatible with both Android and Apple phones or can be synced with any computer with internet access. Individuals without access to a compatible device will be given paper logs and instructed to record their activity counts provided by the activity monitor on a daily basis.

Active Living counseling

The Active Living counseling program will consists of 12 weekly group educational sessions, facilitated by project interventionists. Interventionists will be trained in delivery of the ALED program. These sessions will involve discussion of topics related to increasing physical activity, including: identifying and overcoming barriers, setting goals, social support, and time management.

Facility Access

Subjects will have access to the exercise lab in the UT Southwestern Depression Center consisting of equipment for aerobic exercise (treadmills, stationary bikes, etc.). Subjects can schedule times to access the facility. The facility will be staffed by the Exercise Interventionist or PI at all times.

7.2 Staff Training

The study staff will be trained and certified as specified in the Manual of Procedures and Study Tools Manual. Training will cover protocol-specific training as needed (e.g., assessments, study interventions, fidelity to the protocol and safety procedures, data management and collection, research procedures including understanding reliability and validity, and problem solving), as well as any IRB-required trainings

8.0 STATISTICAL ANALYSES

8.1 Primary Analyses

Based on recommendations of Leon et al.,⁴⁰ the Aims 1 and 2 will examine the feasibility of implementing a physical activity intervention for breast cancer survivors. The feasibility of the study will be assessed by the following criteria:

- 1) Screening - the number of subjects screened through the web-based questionnaire and the percentage of those screened who meet program eligibility requirements
- 2) Recruitment - the percentage of screened subjects that are ultimately enrolled
- 3) Intervention Compliance – defined as percentage of weekly exercise does completed by participants randomized to the exercise condition
- 4) Retention – defined as percentage of assessments completed

Consistent with Aim 3, we will conduct a data analysis examining the effects of the intervention on physical activity and depressive symptoms. A mixed-effects repeated measures model will be used to analyze the primary outcome measures (minutes of MVPA and QIDS-C scores). The independent variables in the model will be time (weeks 1, 13, and 25)(within-subjects factor). The model will allow for random slopes and intercepts while all other factors will be fixed effects. The baseline value of the dependent variable will be included as a covariate as will the other potential covariates if needed [age, race, gender, history of depression]. The need for higher order times terms or the transformation $\log(\text{time}+1)$ to obtain a better fitting model will be considered. The goodness of fit of the final model will be investigated. The analysis will use all available data from all randomized patients with at least one post-baseline visit (i.e., modified “intent to treat” sample) and all tests will be two-sided with alpha of .05 used for significance. The hypothesis will be tested by the significance of the time effect main effect. The analysis will be done using SAS Proc Mixed. Statistical analysis will be completed by [name] within the Center for Depression Research and Clinical Care.

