2.0 STUDY OBJECTIVES

2.1 Although multiple strategies for increasing physical activity have proven efficacious, little is known about the optimal intervention strategies for breast cancer survivors or how those interventions can be effectively implemented in real-world settings. The proposed pilot project will assess the implementation of evidence based strategies for increasing physical activity among breast cancer survivors. Results from this pilot project will support future grant applications. These future studies will utilize multi-phase optimization strategy (MOST) to identify the optimal combination of intervention strategies to increase physical activity among breast cancer survivors.

Aim 1. Evaluate the feasibility of screening and subject recruitment through targeted mailings to breast cancer survivors using the UT Southwestern cancer registries.

Aim 1A. Assess the percentage of contacted survivors completing online questionnaires.

Aim 1B. Assess the percentage of respondents meeting eligibility criteria (< 150 minutes of physical activity per week and ≥ 8 on the PHQ-9).

Aim 1C. Assess the percentage of eligible respondents enrolled in the physical activity intervention.

Aim 2. Evaluate the feasibility of implementing a multi-component physical activity intervention in breast cancer survivors with significant depressive symptoms.

Aim 2A. Physical activity program compliance.

Aim 2A.a. Assess the percentage of physical activity classes attended

Aim 2A.b. Assess the percentage of days of use of the self-monitoring device

Aim 2B. Participant-reported program satisfaction

Aim 3. Conduct preliminary analysis of changes in physical activity and depressive symptoms following the physical activity intervention.

Hypothesis 1. Participants in the physical activity program will demonstrate increases in physical activity at three and six months

Hypothesis 2. Participants in the active living program will demonstrate decreases in depressive symptoms at three and six months post-baseline.

Cancer Relevance: This project simultaneously targets two factors (depression and inactivity) related to poor outcomes in breast cancer survivors and provide important information on how to effectively address these risk factors in a real-world setting.

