3.0 STUDY DESIGN

3.1 Overview of Study Design

The research project is a pilot study to assess the effects of a multi-component intervention in increasing physical activity among breast cancer survivors with depression. Breast cancer survivors listed in the UT Southwestern Simmons Cancer Center cancer registry will be contacted via mail and invited to complete a brief online questionnaire. Those indicating insufficient levels of physical activity and increased depressive symptoms will be invited to participate. The 12-week physical activity intervention will consist of three evidence-based strategies: print-based materials, active living classes, and activity self-monitoring.

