3.2 Duration of Study and Study Timeline

Recruitment of participants will begin in February 2016. We aim to recruit a cohort of 10 subjects in per month through June 2016 for a total of 50 subjects.

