5.4 Treatment and Study Intervention

Participants will be enrolled in the physical activity intervention described in sections 7.0 Assessments will be conducted based on the schedule outlined in section 6.0. Qualified, trained, and certified personnel will conduct clinician-rated assessments (all assessments which are not self-report). During the trial, the outcome assessments will be obtained at Weeks 1, 13, and 25. Participants will be asked to wear an accelerometer during Weeks 1, 13 and 25. If the participant is not able to come to the site and (s)he agrees, some assessments and/or visits may be conducted by phone, by mail, or at appropriate off-site locations, and/or on participants' or other off-site computers via the secure study website(s) if access to a computer with internet service is available. Detailed descriptions of the assessments are provided in section 6.0.

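### Sections 8.1 and 3.1 present a single-arm change over time as an effect of the intervention, which the planned time test cannot show

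*Combined protocol and SAP*

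**What the plan says.** Section 8.1 introduces the Aim 3 analysis as "examining the effects of the intervention on physical activity and depressive symptoms". It names minutes of MVPA and the QIDS as primary outcome measures, fits a mixed model whose only design factor is time (Weeks 1, 13 and 25), and gives the decision rule: "The hypothesis will be tested by the significance of the time effect main effect", two-sided at 0.05. Section 3.1 calls the project "a pilot study to assess the effects of a multi-component intervention in increasing physical activity among breast cancer survivors with depression".

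Aim 3 in section 2.0 is more careful: "Conduct preliminary analysis of changes in physical activity and depressive symptoms following the physical activity intervention". Its two hypotheses say that participants will show more activity and fewer depressive symptoms at three and six months. The study summary also describes a preliminary analysis of changes and makes feasibility the primary objective.

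On the design, section 5.4 says "Participants will be enrolled in the physical activity intervention described in sections 7.0" and section 7.1 says "All participants will receive print-based education focused on physical activity". No comparator and no allocation procedure is described. Section 8.1 nevertheless refers twice to randomized participants, once when defining compliance and once when defining the analysis sample.

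**The concern.** A significant time effect shows that scores changed. With no comparison group it does not show why. Three other causes of change are built into this design or population:

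- **Natural recovery.** Depressive symptoms can change over six months without the intervention.
- **Season.** Entry is confined to February to June 2016.
- **Regression to the mean.** Everyone enters on low reported activity, and some on a raised PHQ-9. Any regression would run in the direction of the hypotheses: activity up, symptoms down.

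No section limits the causal reading or mentions any of the three. The covariates in 8.1 (baseline value and, if needed, age, race, gender and history of depression) include neither season nor concurrent treatment, although current antidepressant treatment is a route of entry under 4.1. The stake is what the trial may conclude. The results are meant to support future grant applications, and the wording of 8.1 would allow p<0.05 for time to be described there as an intervention effect.

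**Working it through.** **1. What the time effect contains.** In one arm, mean change = intervention effect + natural course + seasonal change + regression to the mean. The trial estimates the sum. Nothing in the model separates the terms.

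**2. Calendar.** Section 3.2 says "Recruitment of participants will begin in February 2016" and runs through June. Week 13 starts 84 days after Week 1 (12 × 7) and Week 25 starts 168 days after (24 × 7).

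| Baseline | Week 13 | Week 25 |
|---|---|---|
| 1 February | 25 April | 18 July |
| 1 March | 24 May | 16 August |
| 30 June | 22 September | 15 December |

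At 168 days every participant has moved to another season. At Week 13 this is not universal: a 1 March baseline reaches 24 May, still in meteorological spring. The documents do not show which way any seasonal effect would run.

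**3. Regression to the mean on the QIDS (illustration).** Screening uses the PHQ-9; the outcome is the QIDS, first measured at a separate baseline. Spurious change therefore arises only if the screening score correlates less with the later QIDS than with the baseline QIDS:

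spurious change (SD) = [φ(z)/p] × fall in correlation,

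where p is the fraction passing the screen and z its normal cut-off. Both inputs are assumed. Section 4.3 estimates that at least 33% of respondents meet the eligibility criteria together, not the PHQ-9 criterion alone. The formula treats every entrant as selected on the score.

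| p | φ(z)/p | fall 0 | fall 0.10 | fall 0.20 |
|---|---|---|---|---|
| 0.33 | 1.10 | 0 | 0.11 | 0.22 |
| 0.50 | 0.80 | 0 | 0.08 | 0.16 |

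If half entered on antidepressant treatment alone and contributed no drift (assumed), the non-zero range of 0.08 to 0.22 halves to 0.04 to 0.11.

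**4. What drift from any source does to the test.** The plan's N reproduces: 10 per month × 5 months = 50, and 150 × 0.33 = 49.5. As a stand-in for the time effect, take a two-sided paired t test from baseline to Week 13 with all 50 measured, no intervention effect, drift d in SD units and within-person correlation r. The standardised difference is d/√(2(1 − r)), with 49 degrees of freedom. For d = 0.22 and r = 0.5 it is 0.22/√1 = 0.22.

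| Drift d (assumed) | r = 0.3 | r = 0.5 | r = 0.7 |
|---|---|---|---|
| 0.10 | 0.09 | 0.11 | 0.15 |
| 0.20 | 0.22 | 0.28 | 0.43 |
| 0.22 | 0.25 | 0.33 | 0.50 |
| 0.30 | 0.42 | 0.55 | 0.77 |

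Entries are probabilities of p<0.05 when the intervention does nothing. With zero drift the figure is 0.05.

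**The case against.** The best defence is that this is a feasibility pilot whose Aim 3 is labelled preliminary. The sentence in 8.1 ties itself to Aim 3, the hypotheses are about within-person change, and a time effect is a proper test of those. No go/no-go decision depends on it, and the planned follow-on work concerns the best combination of strategies. Screening and outcome instruments differ, and there is a separate baseline, both of which weaken regression to the mean. All of this stands and keeps the point to one of wording and interpretation. It does not remove the effects language in 3.1 and 8.1, the formal test attached to it, or the absence of any limiting sentence.

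A reader might infer more than the documents support:

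- **That Aim 3 itself claims an effect.** It does not; only 8.1 and 3.1 do.
- **That most entrants were selected for a high PHQ-9.** Section 4.1 admits a PHQ-9 of 8 or more or current antidepressant treatment, and no split is given.
- **That all follow-up is in a different season from baseline.** This holds at Week 25 but not for everyone at Week 13.
- **That regression to the mean would match the whole d = 0.22 cited in section 1.0 for cancer survivors.** Only the extreme corner of the assumed range reaches it, zero is possible, and the same section cites 0.83 to 1.39 for exercise as a treatment for depression.
- **That a control arm is needed within this N.** At 25 per arm, power for d = 0.22 would be 11.9%, and 80% power needs 325 per arm.

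**Conclusion.** The point holds as a mismatch between the claim and the design. On the reading the documents best support, there is one arm and time is the only design factor, so a significant time effect is evidence of change and not of efficacy. Sections 8.1 and 3.1 go further than Aim 3 and the study summary.

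The size of the problem is not known. For regression to the mean on the QIDS, 0 to about 0.22 SD is an illustration that rests on an assumed selection fraction, an assumed fall in correlation and all entrants being selected on the score. Nothing in the documents allows a figure for MVPA, season or natural recovery. No number in the plan is wrong on this account, and N = 50 is unaffected. The correction should be made because it governs what the trial may conclude and costs little.

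**What to change.** 1. In 8.1 and 3.1, replace the effects wording with *within-person change from baseline following the intervention*, in line with Aim 3.
2. Make the estimated change at Weeks 13 and 25, with its 95% CI, the main output for MVPA and the QIDS.
3. State in 8.1 that the time test will not be read as evidence of efficacy, and name natural recovery, season and regression to the mean as the reasons.
4. Report QIDS change descriptively by entry route: PHQ-9 of 8 or more, and antidepressant treatment alone. Only the first group was selected on a high score. The second has PHQ-9 scores below 8 by construction, so any regression there could run the other way. The table informs the reader but does not correct the estimate, and it does not address natural recovery.
5. Reconcile the two references to randomized participants in 8.1 with the single-arm design.

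A table of change by start month is not worth adding. It would have about 10 people per cell (50/5), all followed for the same interval, and could not separate season from intervention.

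The cost is edits to two sections, one small table from data already collected, and a more modest claim. Sample size, visits and Aims 1 and 2 do not change.

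### With no residual covariance named, the random-slope model in section 8.1 can tie the two 12-week changes to one variance and misstate the interval for the three-month change

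*Combined protocol and SAP*

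**What the plan says.** Section 8.1 plans a mixed-effects repeated measures model in SAS Proc Mixed for minutes of MVPA and the QIDS score. On the mean structure it says "The independent variables in the model will be time (weeks 1, 13, and 25)(within-subjects factor". On the random part it says "The model will allow for random slopes and intercepts while all other factors will be fixed effects". It gives no residual covariance structure and no covariance structure for the random effects. It leaves some room: "The need for higher order times terms or the transformation" log(time+1) will be considered, and "The goodness of fit of the final model will be investigated". No method or decision rule is attached to either. The baseline value of the outcome is also to be entered as a covariate.

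The test is the overall one: "The hypothesis will be tested by the significance of the time effect main effect", and "all tests will be two-sided with alpha of .05 used for significance". No visit-specific contrast is written. Yet Hypothesis 1 in section 2.0 reads "Participants in the physical activity program will demonstrate increases in physical activity at three and six months", and Hypothesis 2 names the same two times for depressive symptoms.

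Section 3.1 places the intervention in the first interval: "The 12-week physical activity intervention will consist of three evidence-based strategies". Section 7.1 gives 12 weekly group sessions. It states no end for the activity monitor, the book or access to the exercise facility.

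**The concern.** Weeks 1, 13 and 25 are exactly 12 weeks apart. A personal straight line in weeks, plus independent residuals of constant variance, gives the first and second 12-week changes the same variance whatever the data show. The design gives reason to doubt that equality: the classes run in the first interval and have ended in the second. If people differ in how much they respond by Week 13 and then hold their level, a straight personal slope cannot represent it.

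At stake is the interval for the three-month change, which both Aim 3 hypotheses name. It would be too narrow if the first change is the more variable and too wide if it is the less variable. The Week 13-25 change, which shows whether gains last, would be misstated in the opposite direction.

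**Working it through.** **The plan's own figure.** The documents give no SD, power or standard error for the change analysis. The only figure to reproduce is the sample size: 10 per month for five months (section 3.2) = 50; section 4.3 gives 33% of 150 = 49.5, about 50.

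**Inputs from the documents.** Visits at Weeks 1, 13 and 25; random intercept and slope; two-sided alpha .05; n = 50. **Assumed:** complete data, categorical time in the mean, independent residuals, no baseline covariate, and the change variances below.

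**Step 1: the constraint.** Let Y(t) = b0 + b1·t + e, with residual variance s. The variance of a change over a gap g is g²·Var(b1) + 2s. Both gaps are 12, so both variances equal 144·Var(b1) + 2s.

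**Step 2: the standard error the model uses.** Let D1 and D2 be the Week 1-13 and Week 13-25 changes, with true variances v1 and v2. Let L = D1 + D2 and Q = D2 − D1. The model makes L and Q uncorrelated. When the fit is not on a boundary it matches Var(L) and Var(Q), which sum to 2(v1 + v2). Since D1 = (L − Q)/2, the model variance of D1 is (v1 + v2)/2, so SE² = (v1 + v2)/(2n). As a check, one simulated data set of 50 had v1 = 2.324 and v2 = 0.994: √(3.318/100) = 0.182, and a REML fit gave 0.182. The unstructured value is √(2.324/50) = 0.216. A log(time+1) slope gave 0.205.

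**Step 3: size of the error, linear time.** Let r be the between-person variance in response divided by the noise variance of a change score, with no variance added after Week 13. Then v1 = 1 + r and v2 = 1. The ratio of model SE to true SE is √[(2 + r)/(2(1 + r))] for the Week 13 change and √[(2 + r)/2] for the Week 13-25 change. The actual size is 2[1 − Φ(1.96 × ratio)].

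| r (assumed) | Week 13 SE ratio | Actual size at .05 | Week 13-25 SE ratio |
|---|---|---|---|
| 0.25 | 0.949 | 6.3% | 1.06 |
| 0.5 | 0.913 | 7.4% | 1.12 |
| 1 | 0.866 | 9.0% | 1.22 |
| 2 | 0.816 | 11.0% | 1.41 |

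The Week 25 minus Week 1 standard error is right, because Var(L) is matched.

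**Step 4: the opposite direction.** Let k = SD(D1)/SD(D2). If k is 0.8, 0.67 or 0.5, the Week 13 SE ratio is 1.13, 1.27 or 1.58, and the size is 2.7%, 1.3% or 0.2%.

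**Step 5: the permitted log(time+1) slope.** The gaps become ln 14 − ln 2 = 1.946 and ln 26 − ln 14 = 0.619. Their squares are 3.787 and 0.383, a ratio of 9.9, so this model implies a larger first-interval variance. Fitted to the four scenarios of step 3 (intercept variance set equal to the change-score noise variance), it makes the Week 13 SE 3%, 5%, 8% and 11% too small, with sizes 5.7%, 6.3%, 7.1% and 8.0%. The Week 13-25 SE is 2%, 3%, 7% and 13% too large. The Week 25 minus Week 1 SE becomes 2-5% too large.

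**Step 6: simulation, linear slope, n = 50, 5,000 replicates per scenario.** With k from 0.67 to 2 and the correlation of the two changes from −0.4 to 0.3:

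- Three-month contrast: 1.2% at k = 0.67, 4.4-4.8% at k = 1, 7.1-7.8% at 1.25, 8.4-9.8% at 1.5, and 11.3-11.9% at 2.
- Same contrast, unstructured covariance: 4.2-5.4% throughout.
- Overall 2-df time test: 4.4-6.4%.
- Week 25 minus Week 1: 4.3-5.7%.

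**The case against.** Four objections carry weight.

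- **The planned test is nearly untouched.** Section 8.1 tests the time main effect, whose size stays close to nominal. The distorted contrast is one that 8.1 never writes. This stands, and a reader should not infer that the planned test is invalid. But the hypotheses name three months, so that estimate and its interval will be wanted.
- **The equality is not fixed by the text.** It depends on linear weeks and an unstated residual structure, and 8.1 allows log(time+1) and a fit check. In the step 5 scenarios the log slope also fits better than the linear one, so a fit comparison would favour it. This stands too. The log slope cuts the Week 13 error but imposes a pattern of its own, and 8.1 names no other covariance to compare.
- **Nothing shows that the variances differ.** No SD of change is given, and monitor use and facility access have no stated end. The error may be small, absent or reversed. It is therefore too strong to say that the three-month error bars are wrong.
- **Baseline may enter only as a covariate.** Two outcome rows per person then give three distinct moments for four covariance parameters. A reader might infer a second source of wrong standard errors. That does not follow: the model can reproduce any two-by-two covariance, so its fixed-effect standard errors match an unstructured fit. The parameters are redundant and software may warn, but no equal-variance constraint arises.

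One further reading needs separating. If time enters the mean as a single straight line, the three-month change is half the six-month change by construction, and the problem is then the mean and not the variance.

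**Conclusion.** The point holds conditionally. A linear-week random slope with independent residuals gives the two 12-week changes one variance, and the three-month standard error comes from their average. Under the assumed range (r from 0.25 to 2, nothing added after Week 13) it is 5-18% too small under linear time and 3-11% too small under log time; if the second interval is the more variable, it is too large. These figures rest on complete data and on variances that the documents do not give. The priority is minor to moderate: Aim 3 is a preliminary analysis in a 50-person feasibility pilot, but the repair is cheap and protects an estimate that both hypotheses name.

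**What to change.** In section 8.1, replace the random intercept and slope with categorical time and an unstructured covariance over Weeks 1, 13 and 25: a REPEATED statement with TYPE=UN by participant, and Kenward-Roger degrees of freedom. Keep Week 1 as a response, and so do not also enter the baseline value as a covariate. State that the Week 13 minus Week 1 and Week 25 minus Week 1 contrasts will be reported with their intervals, alongside the overall time test.

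The cost is a few lines of wording and two more covariance parameters (six instead of four), which is negligible at n = 50 with three visits. No new data are needed.
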